14.1 SAMPLE SIZE AND RECRUITMENT

This is a feasibility pilot study, which will test the feasibility of PVC/VT foci mapping with Vivo system and catheter ablation in unselected patients without structural heart disease, eligible for PVC/VT ablation. Therefore, no power calculation has been done and the number of patient recruited will be of 15 which are deemed sufficient by the CI and Co-PIs on a clinical basis.

The estimated recruitment period for the trial will be of 6 months. We estimate that this sample size is attainable in practice, as the number of PVC/VT ablation procedures per year performed within the Trust is around 100. We also included patients with previous PVC/VT ablation in order to maximise chances of recruitment. This pilot is performed with the intention to plan a prospective multi-operator/multicentre trial which is adequately powered. We will aim to compare the procedure parameters as well as the outcome of this trial to age & gender matched procedures of the same operators from the last 5 years' database.

14.2 ENDPOINTS

14.2.1 Primary endpoints

Safety:

- Absence of acute adverse events due to the use of VIVO system during PVC/VT ablation
- Safety endpoint of the entire mapping and ablation strategy

Efficacy:

- To assess the efficacy of VIVO to decrease procedure time as compared to standard of care ablation procedures.

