4.3.2 Procedure Requirements

4.3.2a Prior to EP Procedure

Prior to the procedure the subject will undergo cardiac and thoracic imaging. This can be in the form of a MRI or CT scan, based on physician preference. Specific MRI and CT scan protocols do not significantly differ from the protocols already in use at the Brompton for pre-procedure roadmap scan. The recorded DICOM images should be provided the physician to upload into VIVO for future segmentation. The Mortara 12-lead Holter will be used to record the patient’s PVCs templates (with their respective frequency of presentation). The recorded files will be then imported into Vivo analysis software for the analysis and localization on the pre-reconstructed model. Likewise, the analysis will be done with templates from the Sensis software in the catheter laboratory.

The 3 D Camera will be used to take a 3D image of the patient’s torso after ECG lead placement. This will be merged with the cardiac anatomy from the 3D scan.

4.3.2b During the EP procedure

The EP procedure will be completed per the Institution’s standard of care using a 3D electroanatomical mapping system (CARTO, Biosense Webster).

The information from VIVO analysis will be integrated in the 3D mapping process such that the ablation procedure will be provided with this information, or in post-processing to establish the accuracy of the localization.

Pacing locations can be selected at any time during the procedure based on the physician’s preference.

4.3.2c Registration of EAM to Imaging

Left sided ablations: A Carto mapping catheter will be used to generate a complete fast anatomic map (FAM) anatomic shell of the left ventricle for identification of cardiac structures related to imaging. Imaging should be acquired at End Diastole. Landmarks will include those that are required for the individual procedure, including the papillary muscles if pacing is planned on the papillary muscles.

Right sided ablations: A Carto mapping catheter will be used to generate a complete fast anatomic map of the entire right ventricle and right ventricular outflow tract. Landmarks will include those that are required for the individual procedure.

4.3.2d Identifying the location of PVC or VT Origin

Identification with VIVO: Identifying the location of the PVC or VT foci with VIVO will be done prior to the patient's procedure.

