4.4 MANAGEMENT OF POTENTIAL STUDY RISKS

Risks

There is no additional risk onto the already well-established risks of catheter ablation of PVC/VT/VF.

CT scan (only if patient has a contra-indication for CMR scans)

The scan is acquired in a single breath hold during expiration from the level of the acromial processes to the dome of the diaphragm and starts with the 80 mls injection of contrast agent with Omnipaque 350 mg/ml followed by 20 mls of saline at a flow rate of 5 mls per second.

Cardiac CT performed on retrospective ECG gated CT imaging (end diastole) using tube modulation technique and adjusting the kvp according to BMI (100 kvp if BMI<30 and 120 kvp if BMI >30 kg/m²). There could be adverse reactions to the intravenous contrast agent. Patients with renal impairment would be excluded from this study.

Clinical protocols are in place to manage anaphylaxis which is however very rare.

Mapping with VIVO system and catheter ablation

We anticipate that mapping with VivoTM system will not prolong the overall procedure duration or any technical aspect of the catheter ablation. As it is a non-invasive system intended to provide an accurate localization of the arrhythmia foci, most part of the work will be carried out in a pre-procedural phase (anatomy reconstruction from the pre-acquired scan, ECG template acquisition and arrhythmia foci localization on the virtual model). Also, the radiation exposure time for operator and patient is overall comparable to conventional procedures.

We will use an amended version of the already routinely used consent form for PVC/VT ablation used in the Trust to outline the inherent risk of an ablation for PVCs/VT/VF.

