7.3 DISCONTINUATION/WITHDRAWAL OF PARTICIPANTS AND STOPPING RULES

There are no major additional hazards related to the use of Vivo mapping system to guide the ablation, and the rest of the procedure is carried on using an established ablation strategy. The only difference is in the pre-procedural phase, when Vivo software will be used to localise the ablation targets. Therefore, we do not expect that patients will develop major

side effects related to the intervention tested in this study to warrant withdrawal. However, if patients present with acute medical conditions non-related to the study or new diagnosis are made during the follow-up period, such as active malignant disease, they can be withdrawn from the study. Additionally, patients can be withdrawn on their own request. The patients thus withdrawn from the study will continue to be followed-up regularly in the arrhythmia clinic. There are no major foreseeable circumstances under which the trial will need to be stopped prematurely, other than technical limitations.

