10.3 TREATMENT PROCEDURE

Using the roadmap 3D image information of the CMR or CT scan a standard three-dimensional (3D) reconstruction will be performed (CARTO software package). The CMR or CT scan will be also imported into the Vivo anatomy software to reconstruct the patient's model, necessary for the following localization analysis.

Before the start of the ablation procedure, when still in the ward, the patient will undergo a 12-lead ECG recording (Mortara) while contemporarily on telemetry in order to record the templates of the different PVC/VT morphologies, with also regards to their frequency. Should the patient present no ventricular arrhythmia, a challenge with exercise bike or

intravenous administration of isoprenaline or atropine could be chosen. Finally, a picture of the patient's chest will be taken and imported in the software to match the ECG electrodes' position.

Mapping Vivo non-contact system and ablation procedure

Once the different templates are acquired, they will be imported into the VIVO analysis system, and a final model with foci localization will be generated. The information will be integrated into the 3D mapping system prior to starting the procedure.

After venous vascular access has been gained using an ultrasound-guided approach, an octapolar catheter (Inquiry™, Saint Jude Medical) will be positioned in His-RV position, while a mapping/ablative catheter will be used both for mapping and RF delivery. In case of arrhythmias originating from the LV, it is the operator's choice to use either an arterial femoral access for a retrograde approach or a transseptal access route. In case of left-sided access, as per institutional standard, ACT measurements will be carried out every 30 min with bolus injections of Heparin to achieve an ACT of ≥ 350 sec.

The whole ablative procedure will be carried out according to international guidelines and as for operator expertise and discretion. Achievement of PVC/VT suppression will be documented for all patients for 30 minutes after last RF delivery, with or without IV drug provocation challenge. DCCV may be carried out at the discretion of the operator during the procedure if needed.

Removal of sheaths will be performed as per institutional standard (+/- protamine).

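### The VIVO-specific primary safety endpoint is tied to the ablation, although most VIVO-specific steps, including possible arrhythmia provocation on the ward, come before it

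*Combined protocol and SAP*

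**What the plan says.** Section 14.2.1 lists two primary safety endpoints, and the synopsis repeats both. The first is "Absence of acute adverse events due to the use of VIVO system during PVC/VT ablation". The second is "Safety endpoint of the entire mapping and ablation strategy", with no list of events, time window or criterion. Section 14.2.2 adds safety as a secondary endpoint, also undefined.

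On when VIVO is used, the protocol says:

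- Section 7.3: "The only difference is in the pre-procedural phase, when Vivo software will be used to localise the ablation targets".
- Section 4.3.2: "Identifying the location of the PVC or VT foci with VIVO will be done prior to the" patient's procedure.
- Section 4.4: "most part of the work will be carried out in a pre-procedural phase".
- Section 10.3: the ECG templates are recorded on the ward before the ablation starts. If no ventricular arrhythmia appears, an exercise challenge may be used, or "intravenous administration of isoprenaline or atropine could be chosen". The chest picture follows.

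The schedules in sections 6.3 and 10.5 mark the pre-ablation Mortara recording as research, and telemetry and the roadmap scan as routine. On risk, section 4.4 states: "There is no additional risk onto the already well-established risks of catheter ablation of PVC/VT/VF". It does not mention provocation on the ward.

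**The concern.** A safety endpoint attributed to a device should cover the period in which patients are exposed to what the device adds. Here the only primary safety endpoint attributed to VIVO refers to the ablation, while most VIVO-specific steps precede it. Among those steps, the provocation of arrhythmia on the ward is the one that acts directly on the patient.

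An adverse event during that provocation could therefore be recorded in the notes while the trial still reported no acute VIVO-related events under its first safety endpoint. The design is descriptive (section 14), so the count is itself the result. Section 14.1 says the pilot is meant to lead to a powered multicentre trial, so an unclear safety count could be carried into its planning.

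**Working it through.** The plan gives no safety rate, threshold or power calculation, so there is no figure of its own to reproduce. The check is a comparison of the text, followed by a small illustration.

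**Step 1. Is each VIVO-related source of harm counted under the first bullet?**

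| Step | Timing in the protocol | First bullet, natural reading |
|---|---|---|
| Research Mortara recording for templates | Ward, before ablation (10.3; marked research in 6.3 and 10.5) | Not counted |
| Exercise or intravenous provocation if no arrhythmia appears | Ward, before ablation (10.3) | Not counted |
| Chest picture and VIVO analysis | Before ablation (4.3.2, 10.3) | Not counted, but no hazard identified |
| VIVO location used in the 3D map to guide ablation | Effect arises during ablation (4.3.2, 10.3, 11.2) | Counted |
| CT or CMR roadmap scan | Before ablation, marked routine (6.3, 10.5) | Not clearly VIVO-specific, so not relied on here |

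**Step 2. Does another provision settle the matter?**

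- Second primary bullet: mapping could include VIVO mapping before the procedure, but nothing states when counting starts or what counts. It is also not specific to VIVO, so it would not correct the result of the first bullet.
- Secondary safety endpoint (14.2.2): no events and no window.
- Recording of adverse events (12.2): all are recorded, so the information is kept. Recording does not decide which events count towards an endpoint.
- Statistical analysis plan (14.3): no safety analysis, event list or window.

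**Step 3. Is the risk section consistent with the procedure section?** Section 4.4 states that nothing is added to the known risks of ablation. Section 10.3 allows provocation on the ward to obtain templates for the VIVO analysis. Section 4.4 does not discuss this step.

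**Step 4. What would one uncounted event do?** Inputs: n = 15 (sections 6.1 and 14.1); one event, which is an assumption. Exact (Clopper-Pearson) 95% limits:

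- Counted: 1/15 = 6.7%. The lower limit is 1 − 0.975^(1/15) = 0.2%. The upper limit p solves (1 − p)^15 + 15p(1 − p)^14 = 0.025, giving p = 31.9%.
- Not counted: 0/15 = 0%. The upper limit is 1 − 0.025^(1/15) = 21.8%.

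**The case against.** The strongest reply has five parts.

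1. **The second bullet may cover the ward steps.** It refers to the entire strategy, and VIVO localisation is mapping. This stands in part. A reader might infer that harm before the procedure falls outside the primary safety endpoint altogether. The documents do not support that, because the second bullet is undefined and does not exclude it. They leave open whether such harm counts.

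2. **The reference to the ablation may name the clinical setting, not a counting window.** Section 10.3 describes the ward work under its treatment procedure heading. This reading is possible, but it is not the natural one: section 10.3 itself places the ward recording before the ablation starts. An endpoint that depends on the choice of reading still needs rewording.

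3. **VIVO also acts during the ablation.** This stands. Section 4.4 says most of the work is pre-procedural, not all. Section 4.3.2 also mentions templates from the catheter laboratory, and the VIVO location guides the ablation. A reader might infer that the first bullet is met by construction, or that essentially all VIVO exposure escapes it. Neither follows, because a misdirected ablation could make the endpoint fail.

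4. **Provocation is optional and not unique to VIVO.** Section 10.3 makes it conditional on the absence of arrhythmia, and also allows drug provocation after the last radiofrequency delivery. This limits the likely number of events. It does not change the fact that provocation on the ward serves the study's template recording and falls before the ablation.

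5. **Events are not lost, and no decision rests on the count.** Both are true: sections 12.2 and 12.3 capture and report events, and no threshold is set. The remaining problem is what the primary endpoint will report.

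**Conclusion.** The concern holds in a limited form. On its natural reading, the first primary safety bullet leaves out an adverse event caused by the VIVO-specific steps before the ablation, and the second bullet does not clearly include it. Harm during the ablation from a wrong VIVO localisation remains covered, and all adverse events are still recorded.

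The conclusion rests on two readings: that the phrase about the ablation limits the events counted, and that the ward recording, marked research, and any provocation done for it belong to the study. The contrast between 1/15 and 0/15 shows the effect of one uncounted event in 15 patients. The intervals overlap widely, and nothing in the documents indicates how likely such an event is. The change should be made because this is a primary endpoint and the correction is simple.

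**What to change.** - **First bullet:** count VIVO-related adverse events from the first VIVO-specific study step (the ward recording and any provocation) to a stated end, such as discharge. Report them by phase: before, during and after the procedure.
- **Second bullet:** define it as all adverse events from that same step to the 3-month visit.
- **Consistency:** make the same change in the synopsis, and reconcile the risk statement in section 4.4 with the ward provocation allowed in section 10.3.

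Discharge and the 3-month visit are suggestions that fit the existing schedule. Other end points would serve if they are stated in advance. The cost is wording only: section 12.2 already has all adverse events recorded, so no new visit or test is needed, although the case report form should show the phase of each event. The downside is that the reported event count may rise.

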3. STUDY SYNOPSIS

Full study title:	VIVO™ non-invasive Time Assessment Protocol
Short study title:	VIVO™ mapping Protocol
Study R&D number:	VIVO-RBH01
Chief Investigator:	[name]
Medical condition/disease under investigation:	Patients undergoing PVC/VT Ablation with structurally normal hearts
Study duration:	9 months
Primary Objective:	
Safety:
 
 • Absence of acute adverse events due to the use of VIVO system during PVC/VT ablation • Safety endpoint of the entire mapping and ablation strategy 
Efficacy:
 
 • To assess the efficacy of VIVO to decrease procedure time as compared to standard of care ablation procedures.
Secondary Objective:	
 • To assess clinical outcome (suppression of reduction of PVCs burden/VT at 3-month F/U) • To assess economical outcome (cost reduction per case)
Study population:	
VIVO Cohort – 15 patients presenting for PVC/VT ablation with structurally normal heart
 
Control Cohort – Retrospective review of historical matched patients within the physician's database that had PVC/VT ablations with structurally normal hearts

Recruitment Target	15 patients
Recruitment Window (Months)	6 months
Methodology:	The study is a non-randomized, single-centre, study designed to evaluate the procedural efficacy of VIVO as compared to standard of care ablation procedures. Up to 15 patients will be enrolled.
Eligibility criteria:	
Inclusion criteria:
 
 1. Subjects who are at least 18 years or older 2. Subjects who are scheduled for PVC/VT ablation procedure 3. Subjects who have signed an IRB/EC approved Informed Consent Form and applicable subject privacy protection authorization per local law 4. Subjects will be selected without regard to gender or age (unless precluded by local regulatory requirements) 5. Subjects with or without cardiac structural disease
	
Exclusion criteria:
 
 1. Reversible causes of PVC/VT 2. Subjects with recent (within 3 months) acute coronary syndrome 3. Subjects who are contraindicated for CT or MRI (must be able to get one)

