14. STATISTICAL DESIGN

This is a prospective, non-randomised, observational study which will recruit 15 non-selected patients with PVC/VT eligible for catheter ablation, without structural heart disease.

Procedural outcomes will be compared to age & gender matched procedures of the same operator from the last 5 years' database.

The statistical design was decided in collaboration with the study PIs and will be descriptive only.

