14.3 STATISTICAL ANALYSIS PLAN

Descriptive statistic data with regard to baseline and procedural variables will be reported; continuous variables will be expressed by mean \pm standard deviation or median and interquartile range (25th, 75th percentile), depending on the normality of distribution; categorical variables will be summarized by frequencies and percentages. The outcome of radiofrequency ablation on the entire cohort of patients will be presented in the form of percentage of patients free from symptomatic or documented arrhythmia or with only mild symptoms related to arrhythmia recurrence.

Depending on the severity of symptoms and documentation of tachycardia during follow-up, patients will be divided into two groups (success/recurrence). Baseline characteristics and procedural variables will be compared between these two groups by student t-tests, Mann Whitney U tests, or Fisher's exact test where appropriate in order to identify those variables associated with better mid/long term outcomes. A two-tailed p value <0.05 will be considered statistically significant. Intra-patient improvement from baseline to 6 months follow-up visit will be assessed by McNemar's test. Freedom from PVC/VT will be assessed as a time-dependent variable using Cox proportional hazard models.

To judge if ablation strategy using Vivo mapping system is as successful in achieving the clinical endpoint, we will compare the procedure parameters as well as the outcome of this trial to age & gender matched procedures of the same operator from the last 5 years' database.

To measure the strength of association between the acute successes (PVC/VT suppression at the end of the ablation) and outcome, a McNemar test will be performed. Data will be analyzed using SPSS version 18 (IBM Corporation).

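### The first primary safety endpoint is worded as an absence of VIVO-related events, with no measure of uncertainty planned, although 0 of 15 leaves rates up to 21.8% compatible with the data (exact two-sided 95% limit)

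*Combined protocol and SAP*

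**What the plan says.** Section 14.2.1 lists two primary safety endpoints. The first is "Absence of acute adverse events due to the use of VIVO system" during the ablation; the second is "Safety endpoint of the entire mapping and ablation strategy". The synopsis (section 3) gives the same two items as primary objectives. Neither comes with a rate, an acceptable limit or a time window, and the second has no list of qualifying events.

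On size, section 14.1 says that "the number of patient recruited will be of 15" and that "no power calculation has been done". The synopsis treats the number as a ceiling: "Up to 15 patients will be enrolled". Section 14 says that the statistical design "will be descriptive only".

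Section 14.3 contains no analysis of adverse events. Its nearest statement is that "categorical variables will be summarized by frequencies and percentages", but that clause sits in a sentence about variables describing baseline and the procedure. No confidence interval is planned anywhere in section 14, and section 14.6 adds nothing.

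**The concern.** An endpoint worded as an absence is either satisfied or not. With 15 patients and no interval beside the count, it can be satisfied by a result that says little about the underlying rate. A report that followed the text could state that a primary safety endpoint was achieved and give the reader no indication of how high a rate the data still allow.

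What is at stake is the strength of the conclusion on a primary endpoint. The conduct of the study and the data collected are not affected.

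**Working it through.** **Inputs.** Number of patients n = 15 (section 14.1), a maximum according to the synopsis. Number of events x = 0, the result that the endpoint describes. Confidence level 95% two-sided. This level is an assumption for safety: the only significance level in the SAP is two-tailed 0.05 in section 14.3, given for the comparison of patients with success and with recurrence. True rates of 5%, 10%, 15% and 20% are illustrative; the documents give no expected rate.

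**The plan's own figure.** There is nothing to reproduce. The 15 was chosen on clinical grounds and has no error rate, event rate or precision target behind it.

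**Step 1: upper limit for 0/15.**
- Exact (Clopper-Pearson), two-sided 95%: 1 − 0.025^(1/15) = 0.218, or 21.8%.
- Exact, one-sided 95%: 1 − 0.05^(1/15) = 0.181, or 18.1%.
- Wilson, two-sided 95%: 1.96² / (15 + 1.96²) = 3.84 / 18.84 = 0.204, or 20.4%.
- Rule of three: 3/15 = 20.0%.

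The limit lies between 18% and 22% whichever convention is used. Whether a rate of exactly 20% is excluded does depend on the convention: the one-sided limit excludes it, the exact two-sided limit does not.

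**Step 2: chance of seeing no event, (1 − p)^15.**
- p = 5%: 0.95^15 = 0.463
- p = 10%: 0.90^15 = 0.206
- p = 15%: 0.85^15 = 0.087
- p = 20%: 0.80^15 = 0.035

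**Step 3: fewer patients treated.** The exact two-sided limit for zero events is 1 − 0.025^(1/14) = 23.2% with 14 patients and 1 − 0.025^(1/12) = 26.5% with 12.

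**Step 4: the all-or-nothing wording.** One event in 15 (6.7%) would fail the endpoint; its exact two-sided 95% interval is 0.2% to 31.9%. Zero in 15 would satisfy it, with an interval of 0% to 21.8%. The two intervals overlap over most of their length, so the wording separates results that the data hardly separate.

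**Step 5: how many event-free patients a tighter limit needs.** Solving 1 − 0.025^(1/n) < u gives n > ln(0.025) / ln(1 − u). For u = 10% this is 36 patients; for u = 5% it is 72.

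**The case against.** The strongest reply is that the study calls itself an unpowered, descriptive feasibility pilot. The endpoint list is loosely worded throughout: the efficacy item beside it is phrased as an aim, and section 14.2.2 lists the assessment of safety again as secondary. On this view the word *absence* is loose drafting and not a pass/fail claim, and any reader who sees 0/15 can work out the limit.

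Part of this stands. A reader might infer several stronger things that the documents do not support:
- *That 0/15 will be declared safe or the endpoint declared met.* No success criterion or decision rule is written. The earlier VIVO cohorts in section 4.2 are described as free of complications without an interval, which makes the inference understandable, but it remains an inference.
- *That the SAP commits safety to percentages only.* The percentages clause concerns baseline and procedural variables. The safety analysis is unspecified.
- *That rates above 20% cannot be excluded, without qualification.* This holds for the exact two-sided limit and, narrowly, for Wilson, but not for the one-sided limit.
- *That an overstated conclusion would pass into the later multicentre trial.* Section 14.1 says that trial is to be adequately powered, and nothing says that 0/15 will serve as its safety evidence.

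The pilot label does not dispose of the point. Safety is listed as primary, and an exact interval is itself a descriptive statement of precision that needs no power calculation. Nor do the earlier cohorts fill the gap. Pooling 0/20 and 0/22 would give 1 − 0.025^(1/42) = 8.4%, but the plan proposes no pooling, and in the second cohort VIVO was analysed after the procedure and so could not have guided it.

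It is also fair to say that an interval is only as good as the event definition. Section 12 leaves causality to the investigators and gives no criteria for separating a VIVO-related event from a complication of the ablation.

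**Conclusion.** The point holds as a matter of endpoint wording and missing precision. Zero events in 15 patients would satisfy the first primary safety endpoint as written, while the exact two-sided 95% upper limit is 21.8% (18.1% one-sided), and higher if fewer than 15 are treated. A true rate of 5% would give that result in nearly half of such studies.

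This rests on all 15 patients being treated and assessed, on independent patients with a common event rate, and on the two-sided 95% convention. It does not rest on any claim about how the investigators intend to interpret zero events, because the documents do not say. The study remains valid without the change. It is a cheap improvement to what can be concluded on a primary endpoint.

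**What to change.** 1. In section 14.2.1 and the synopsis, restate the first safety endpoint as the number and proportion of patients with an acute adverse event attributed to VIVO, with an exact (Clopper-Pearson) two-sided 95% confidence interval. State the time window that counts as acute and how attribution to VIVO is decided.
2. In section 14.3, add that zero events will be reported as none observed in n patients, together with the upper limit for the n actually treated (about 22% for 15), and not as absence of risk.
3. Report the safety endpoint for the whole mapping and ablation strategy with the same type of interval, after listing the events and the period that it covers.

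The cost is a few lines of text. Section 12.2 already requires all adverse events to be recorded in the CRF, so no extra patients, visits or data items are needed for the interval. The downside is a less favourable safety statement.

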4. INTRODUCTION

4.1 BACKGROUND

Accurate localization of the origin of focal ventricular arrhythmias is a prerequisite to successful catheter ablation¹. Nevertheless, mapping and determining the arrhythmic foci is time consuming, invasive and difficult. Catheter ablation guided by VT activation mapping has evolved to treat scar-related arrhythmias with up to 75% success rate after successful mapping procedures. However, non-sustained, non-inducible, or hemodynamically unstable VTs cannot be mapped with this technique. Alternatively, EP substrate mapping during sinus rhythm (SR) identifies the scar EP substrate based on low voltage and the presence of fractionated EGMs and late potentials (LPs). Conventionally, pre-procedural diagnosis and localization of cardiac arrhythmias has been done by the 12 lead ECG ². However, 12-lead ECG arrhythmia-origin algorithms have limitations and may negatively influence ablation outcomes. For example, erroneous identification may result in unnecessary mapping and failure to identify the treatable target ³.

VIVO was developed to easily determine the location of PVC/VT foci and to reduce mapping/identification time. VIVO improves upon the non-invasive 12 lead ECG by combining the ECG data with an already acquired CT/MR image and a 12 lead ECG to create a patient specific model, thus improving the localization accuracy ⁴⁻¹⁰.

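### Procedure time, the primary efficacy measure, has no start or stop rule common to both cohorts, so the comparison cannot be shown to be like for like and a saving may be time moved to the preparation phase

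*Combined protocol and SAP*

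**What the plan says.** The efficacy endpoint in 14.2.1, repeated in the synopsis, is "To assess the efficacy of VIVO to decrease procedure time as compared to standard of care ablation procedures". Sections 5.1 and 5.2 also speak of a shorter procedure, and 5.2 links the expected cost reduction per case to it. Cost reduction per case is a secondary endpoint in 14.2.2.

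Two related terms appear, also undefined. Section 4.1 says VIVO was developed "to reduce mapping/identification time", and 4.4 expects no lengthening of the overall procedure.

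On when the VIVO work is done:
- 4.3.2d: "Identifying the location of the PVC or VT foci with VIVO will be done prior to the" procedure.
- 4.4: "most part of the work will be carried out in a pre-procedural phase".
- 10.3: ECG templates are recorded on the ward and a chest picture is taken, then "The information will be integrated into the 3D mapping system prior to starting the procedure".
- 4.3.2a, pointing partly the other way: "Likewise, the analysis will be done with templates from the Sensis software in the catheter laboratory".

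On in-lab steps for study cases, 4.3.2c requires right-sided cases to "generate a complete fast anatomic map of the entire right ventricle and right ventricular outflow tract", with a matching left-ventricular map for left-sided cases. Section 10.3 states: "Achievement of PVC/VT suppression will be documented for all patients for 30 minutes after last RF delivery".

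Controls are age- and gender-matched procedures of the same operator from the last five years (6.1, 14, 14.3). How their times were recorded is not stated. Section 14.3 says procedure parameters will be compared with these controls but names no method for procedure time.

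**The concern.** One cohort is prospective and the other is read from old records. Without a written clock, each may be timed by a different convention. The clock could also be chosen after both sets of times have been seen.

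Two features of the design make this more than a missing detail. First, VIVO shifts localisation work out of the laboratory. An in-lab clock would credit VIVO with the mapping time it removes and would not charge it for the preparation it adds. Second, total procedure time mixes the part VIVO is meant to shorten with steps that VIVO does not affect, namely the anatomic map and the observation period. If those steps differ between cohorts, or are counted differently, they enter the result as if they were a device effect.

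The only efficacy endpoint in 14.2.1 and the cost endpoint both depend on this, and 14.1 says the pilot is meant to lead to a powered trial. An ambiguous time estimate would carry into that design.

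**Working it through.** The plan has no figure to reproduce. Section 14.1 states that no power calculation was done, and no SD, effect size or number of controls is given. The check therefore writes out what the recorded difference contains and then sizes the one component for which the protocol gives minutes.

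**Decomposition.** For VIVO minus control:

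- recorded difference = Δ + (w_V − w_C) + (m_V − m_C)
- difference in total work = recorded difference + p

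Here Δ is the change in the part of the procedure VIVO can affect, w is post-RF waiting that is counted, m is anatomic-map time, and p is VIVO-specific preparation not already on the clock.

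**What the documents fix.**
- p: not quantified, and no provision is made to record it. It is mostly off any in-lab clock by the protocol's own description (4.3.2d, 4.4, 10.3). Analysis of laboratory templates (4.3.2a) could fall on the clock.
- w_V: 30 minutes if the observation counts, 0 if it does not. The documents do not say which.
- w_C: unknown. Assume controls waited between 0 and 30 minutes.
- m_V: required, duration not given. m_C: not stated.

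**Range of the observation term.**
- Counted in VIVO cases, not waited or not counted in controls: 30 − 0 = +30 minutes, against VIVO.
- Not counted in VIVO cases, waited in full and counted in controls: 0 − 30 = −30 minutes, in favour of VIVO.
- Same wait, same rule: 0.

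Leaving out p favours VIVO. Counting the wait in VIVO cases only works against it. The net direction is unknown.

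**How 30 minutes compares with the study's precision.** Assumptions, none from the plan except the 15 VIVO patients: 15 controls, a common SD of 30 to 90 minutes, and a two-sample t-test. Section 14.3 does not specify that test for this comparison.

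- 95% CI half-width = t(0.975, 28) × SD × √(1/15 + 1/15) = 2.048 × 0.365 × SD = 0.748 × SD
- Noncentrality for a 30-minute offset = 30 / (0.365 × SD)

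| SD (min) | CI half-width (min) | Noncentrality | P(two-sided p<0.05) with a 30-min offset in one cohort and no true difference |
|---|---|---|---|
| 30 | 22 | 2.74 | 0.75 |
| 45 | 34 | 1.83 | 0.42 |
| 60 | 45 | 1.37 | 0.26 |
| 90 | 67 | 0.91 | 0.14 |

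At SD 30 the offset exceeds the half-width, and at SD 45 it is nearly as large. At SD 90 random error dominates. With a zero offset the probability is the nominal 0.05.

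**The case against.** The strongest reply has three parts.

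**The cohorts may well be alike in the laboratory.** Section 7.3 says the pre-procedural phase is the only difference and the rest follows an established strategy. Section 4.3.2b has the procedure done to the institution's standard of care, and Section 14 takes controls from the same operator. This stands. A reader might infer that the comparison is not like for like because of the map and the 30 minutes, but the documents do not support that. They do not describe control practice, and these passages make equal practice plausible. They do not establish it, and they say nothing about how either cohort is timed.

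**Moving work out of the laboratory is the declared aim.** Section 4.3.1 argues for less procedural time, procedural cost and radiation exposure. Laboratory time alone is a legitimate endpoint, so this stands too. It has to be stated, however, and it does not answer the cost endpoint, where preparation is a real input. Some preparation is not VIVO-specific: the roadmap scan is marked routine in 6.3, and the CARTO reconstruction in 10.3 is standard.

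**The study is a descriptive pilot.** Sections 14 and 14.1 explain the absence of a power calculation. They do not remove the need to define what is being described.

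**Conclusion.** The point holds in this form: the endpoint has no common start and stop rule, VIVO preparation is mostly done before the procedure with no provision to record it, and the place of the 30-minute observation in the clock is unstated. Followed as written, the study cannot separate time saved from time moved, and its cost estimate could leave out VIVO preparation.

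The possible distortion from the observation period is 0 to 30 minutes in either direction, assuming controls waited 0 to 30 minutes. The preparation and map components cannot be sized from the documents. The probabilities in the table are conditional on assumed SDs, 15 controls and an unspecified test; the conclusion does not rest on them.

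Two stronger readings should be avoided. A reader might infer that all VIVO work falls outside the clock, but no clock is defined, and the laboratory-template analysis in 4.3.2a could fall inside one. A reader might also infer that preparation cancels the saving, but the documents give minutes for neither.

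**What to change.** 1. In 14.2.1, define procedure time as first vascular access to last RF delivery, read from laboratory or CARTO time stamps by the same rule in both cohorts. State how a case without RF delivery is handled.
2. This interval still contains the anatomic map and any wait before repeat RF. Record anatomic-map time, mapping time to first RF, and post-RF observation (including any wait before repeat RF) as separate components, and show the comparison with and without them.
3. Record VIVO-specific preparation minutes prospectively: VIVO segmentation, ward recording, torso image and analysis. Exclude the routine scan and the standard CARTO reconstruction. Report in-lab plus preparation time next to the primary result, and include preparation in the cost endpoint in 14.2.2.
4. Report how many controls lack the stamps. As a sensitivity analysis, repeat the comparison using a laboratory-log time available in both cohorts.
5. Fix these rules before control times are extracted.

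The cost is a few CRF fields, some text in Section 14 and a review of control records. Whether the stamps exist for all five years is not known from the documents, hence item 4. Patient care does not change. The sponsor should accept that total time may look less favourable to VIVO than in-lab time.
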